7.5 PEN DEVICE COMPLAINT REPORTING REQUIREMENTS

Any devices which are perceived to malfunction (either before or during use) will be returned through a formal complaint system and evaluated to understand the root cause of the failure. All medical device complaints, regardless of whether the medical device complaint is associated with an AE, will be recorded on a complaint form either at the site or using the 24/7 Helpline. This includes potential incidents or malfunctions associated with the use of a medical device product. An incident or malfunction of the PEN is an event that might have led to death or serious deterioration in health, or if it occurred again might lead to death or serious deterioration in health. Sponsor is to be notified immediately of all medical device complaints of the investigator's awareness of the event.

8. Statistical Analysis

8.1 STATISTICAL METHODS

Details of applicable statistical methods will be provided in a Statistical Analysis Plan.

Data from all clinical assessments will be listed and, where appropriate, summarized by cohort using descriptive statistics. Endpoints will be summarized by cohorts and stratifying variables as well.

Summary statistics (arithmetic mean, standard deviation, minimum value, lower quartile, median, upper quartile, maximum value, number of non-missing values) will be presented for continuous variables (absolute values at each time point and changes from baseline if applicable). Frequency statistics (counts and percentages) will be presented for categorical

OPKO Biologics	Protocol for Clinical Study CP-4-004	Page 93 of 133
Effective Date: Date of final electronic approval		

variables. Where appropriate, the presentation of results will include shift tables, plots or confidence intervals.

All statistical evaluations, including efficacy analysis, will be purely exploratory; no hypothesis tests will be conducted, hence this pilot study is not powered.

The assessment of safety will be based mainly on the frequency of AEs, frequency of patients developed anti-MOD-4023 antibody and on the number of laboratory values that fall outside of pre-determined ranges. Data of all safety endpoints will be listed and tabulated.

When all patients complete the Main Study a full analysis (CSR) will be performed based on the SAP.

When all patients will complete the second year of treatment an additional analysis will be performed.

8.2 SAMPLE SIZE

There are no previous pediatric GHD patients for MOD-4023 available to support a formal sample size calculation.

A sample size of 12 patients per cohort has been chosen in this pilot investigation (14 patients will be enrolled to get 12 per protocol evaluable patient in each cohort). Each cohort is stratified according to peak GH levels with up to 10 patients having peak stimulation test GH levels \leq 7 ng/ml and up to 4 patients with peak GH levels [REDACTED] and [REDACTED] ng/ml. The justifications for this sample size are based on rationale about feasibility; precision about the mean and variance; and regulatory considerations as described by (Julious, 2005).

The selected sample size is large enough that there is about a 50% chance of identifying at least 1 patient in the cohort who experiences a treatment emergent adverse event where the nature of the event is such that the true chance that a patient has this type of an event during the treatment period is 5%.

If the true chance that a patient has event during the treatment period is:	then the chance of identifying at least 1 patient who experiences the event during the treatment period is:
5 %	50%
10 %	78%
15 %	90%
20 %	96%

When combining all MOD-4023 patients (n=42) there is about a 94 percent chance of identifying at least 1 patient in the entire group of patients treated with MOD-4023 who experiences a treatment emergent event where the nature of the event is such that the true chance that a patient has this type of an event during the treatment period is 5%.

In fact,

OPKO Biologics	Protocol for Clinical Study CP-4-004	Page 94 of 133
Effective Date: Date of final electronic approval		

If the true chance that a patient has event during the treatment period is	then the chance of identifying at least 1 patient who experiences the event during the treatment period in a sample of size 42 is
5 %	94%
10 %	99.7%
15 %	100%

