NUMBER OF PATIENTS:	Estimated recruitment will be up to 56 patients (up to 14 patients/cohort) into the Main Study. Patients will be divided into two subgroups: Up to 40 patients with peak serum GH levels after stimulation test [REDACTED] ng/ml and up to 16 patients with peak serum GH levels after stimulation test [REDACTED] and [REDACTED] ng/ml. Patients who completed 12 months of treatment in the Main Study and continued to the 12-month Open Label Extension (OLE) period will be eligible to continue into the Long-Term OLE (LT-OLE) period and Long-Term OLE PEN (LT-OLE-PEN) periods until marketing approval in their country, subject to an annual notification to local EC/IRB of continuation of study, where applicable.
DURATION OF STUDY:	The duration of the Main Study is expected to be 12 months for each patient. The OLE period duration will be based on the initial extension of 12 months of active treatment for all patients completing the Main Study which will be extended to LT-OLE and to LT-OLE-PEN on a yearly basis until marketing approval

OPKO Biologics	Protocol for Clinical Study CP-4-004	Page 4 of 133
Effective Date: Date of final electronic approval		

	
in each country. The yearly extension notification will be submitted to local EC/IRB, where applicable

TEST DRUG:	
MOD-4023 is a long-acting modified recombinant human growth hormone which utilizes the CTP technology.
 
In the Main Study and OLE, MOD-4023 will be provided as a solution for subcutaneous (SC) injection containing [REDACTED] or [REDACTED] mg protein¹/ml
 
In the LT-OLE-PEN period, MOD-4023 will be provided as a solution for injection containing [REDACTED] or [REDACTED] mg/mL MOD-4023 in a single patient use, multi-dose, disposable pre-filled pen (PEN).

REFERENCE DRUG (main study):	
Genotropin® 5.3 mg is dispensed in a two-chamber cartridge. The front compartment contains recombinant somatropin, glycine, mannitol, sodium dihydrogen phosphate anhydrous, and disodium phosphate anhydrous. The rear compartment contains m-Cresol and mannitol in water for injections.
 
A delivery device (Genotropin Pen®) will be used for administration of the drug. Active comparator will only be administered in the Main Study.

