4.5 RANDOMIZATION

In the Main Study, patients will be randomized in a 1:1:1:1 ratio to one of 3 different MOD-4023 weekly dose cohorts, or the Genotropin cohort.

OPKO Biologics	Protocol for Clinical Study CP-4-004	Page 45 of 133
Effective Date: Date of final electronic approval		

The randomization will ensure that the study population will consist of: up to 40 patients with peak GH level of [REDACTED] ng/ml (up to 10 patients per cohort) and up to 16 patients with peak GH level of [REDACTED] ng/ml and [REDACTED] ng/ml (up to 4 per cohort);

Randomization will be stratified by:

1. Stimulation tests peak plasma GH level: patients with peak GH level [REDACTED] ng/ml and patients with peak GH level [REDACTED] ng/ml and [REDACTED] ng/ml.
2. Patients with peak plasma GH level [REDACTED] ng/ml will additionally be stratified by age (patients ≤7 years and patients > 7 years), height SDS minus target height SDS (distance from target height SDS ≤ -3 and > -3) and by peak GH levels [REDACTED]. Patients with peak GH levels [REDACTED] can be enrolled in the study. However, these patients have a separate randomization list.

The randomization will be performed via a web-based electronic data capture (EDC) system once all screening data is available and reviewed by the Medical Monitor.

In the OLE period all patients will receive MOD-4023. Patients who received MOD-4023 in the Main Study will continue on the same dose. Patients treated with Genotropin will be switched to MOD-4023 and will be randomized to one of the three MOD-4023 cohorts.

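### The pooled chance of detecting an adverse event is stated for 42 MOD-4023 patients but fits 56; for 42 the 94% should be 88%

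*Protocol*

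**What the plan says.** Protocol section 8.2 (Sample Size) gives no power calculation. It says "A sample size of 12 patients per cohort has been chosen in this pilot investigation", and adds that "14 patients will be enrolled to get 12 per protocol evaluable patient in each cohort". It then describes what this size delivers for safety. For one cohort: "The selected sample size is large enough that there is about a 50% chance of identifying at least 1 patient in the cohort" at a true event rate of 5%, with a table giving 50%, 78%, 90% and 96% at true rates of 5%, 10%, 15% and 20%.

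For the three active cohorts together it says: "When combining all MOD-4023 patients (n=42) there is about a 94 percent chance of identifying at least 1 patient in the entire group", again at a true rate of 5%. A second table follows, with a column headed "then the chance of identifying at least 1 patient who experiences the event during the treatment period in a sample of size 42 is" and the values 94%, 99.7% and 100% at 5%, 10% and 15%. The number 42 therefore appears in both the sentence and the table header.

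The design numbers are given elsewhere. The synopsis says "Estimated recruitment will be up to 56 patients (up to 14 patients/cohort) into the Main Study", and section 4.5 says "patients will be randomized in a 1:1:1:1 ratio to one of 3 different MOD-4023 weekly dose cohorts, or the Genotropin cohort".

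**The concern.** The chance of at least one event in n patients rises with n, so the figure has to be tied to the right number. The pooled values look too high for 42 patients and look like values for the full trial. The full trial includes a cohort that receives Genotropin, not MOD-4023, throughout the Main Study, and those patients cannot reveal a MOD-4023 adverse event in that period.

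Safety is part of the primary objective (section 2.1.1). Section 8.2 also refers to feasibility, precision and regulatory considerations but attaches no numbers to them. The detection probabilities are thus the only quantified property offered for the chosen size. A reader who wants to know how much reassurance to take from an event not being seen among MOD-4023 patients would rely on them, and the error runs in the favourable direction.

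**Working it through.** **Inputs**
- Cohort size: 14 enrolled, 12 evaluable per protocol (section 8.2).
- Allocation 1:1:1:1 to three MOD-4023 cohorts and one Genotropin cohort (section 4.5), so 3 × 14 = 42 on MOD-4023 and 4 × 14 = 56 in total. The 56 agrees with the synopsis.
- True event rates p: 5%, 10%, 15% and, per cohort, 20% (section 8.2).

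**Formula.** With independent patients, P(at least one event) = 1 − (1 − p)^n.

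**Step 1: confirm the formula on the per-cohort table.**

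| p | Printed | n=14 | n=12 |
|---|---|---|---|
| 5% | 50% | 51.2% | 46.0% |
| 10% | 78% | 77.1% | 71.8% |
| 15% | 90% | 89.7% | 85.8% |
| 20% | 96% | 95.6% | 93.1% |

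With n=14 every row agrees to about one percentage point. With n=12 every row falls short by about 3 to 6 points. A Poisson form, 1 − exp(−np), with n=14 gives 50.3 / 75.3 / 87.8 / 93.9%, which fits only the first row. The binomial formula with n=14 is therefore the protocol's basis.

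**Step 2: apply it to the pooled table.**

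| p | Printed for n=42 | n=42 | n=56 |
|---|---|---|---|
| 5% | 94% | 88.4% | 94.3% |
| 10% | 99.7% | 98.8% | 99.7% |
| 15% | 100% | 99.9% | 99.99% |

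At 5% the printed value exceeds the n=42 value by 94 − 88.4 = 5.6 points. At 10% the gap is 0.9 points, visible at the one decimal printed. At 15% the n=42 value still rounds to 100%.

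**Step 3: look for another basis for 94%.** At p = 5%:
- Poisson with n=42: 87.8%.
- n=36 (12 × 3): 84.2%.
- n=48 (12 × 4): 91.5%.
- n=53 (the number SAP section 4.1 says entered the extension): 93.4%.
- n=56: 94.3%.

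Across n = 34 to 63, only 54, 55 and 56 round to both 94% and 99.7%. Of these, only 56 is a planned design number.

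**Step 4: size of the error.**
- Chance of seeing no case at a 5% rate: 100 − 88.4 = 11.6%, against 100 − 94 = 6% as implied. The ratio is 11.6 / 6 ≈ 1.9.
- At a 10% rate: 1.2% against 0.3%.
- Event rate at which 42 patients do give 94% detection: p = 1 − 0.06^(1/42) = 6.5%.

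**The case against.** The arithmetic for n=42 is not in dispute. The case on the other side concerns scope and weight.

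- **Per-cohort table.** Adverse events are analysed in everyone randomized who received at least one dose (sections 8.3 and 8.5), so 14 is the natural denominator, and 42 = 3 × 14 uses the same basis. This stands in substance. The text still calls 12 the chosen size and then credits the selected size with about 50%, so the table needs a label, but its values are sound for 14.
- **Origin of the figures.** No document says that 56 was used. That is correct: it is an inference from the fit. The error at n=42 does not depend on it.
- **Extension exposure.** Genotropin patients are re-randomized to MOD-4023 in the extension, so the number ever exposed may approach 56. This does not rescue the figure, because the sentence and the table header both say 42. If ever-exposed patients were meant, the 42 would be the error instead.
- **Weight.** Section 8.1 describes all evaluations as exploratory and the study as unpowered. No stopping rule, analysis set or enrolment target depends on the 94%. The Main Study is also already complete in this protocol version: section 1.4.1 reports its 12-month outcome. This stands. It lowers the priority of the correction, not its validity.

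**Conclusion.** The concern holds. For the 42 MOD-4023 patients named in the text, the chance of seeing at least one case is 88.4% at a true rate of 5% and 98.8% at 10%, not 94% and 99.7%. The 15% entry is acceptable as rounded. The printed values are those of a 56-patient sample, most plausibly the whole Main Study including Genotropin.

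The overstatement is 5.6 points at a 5% rate, which roughly halves the apparent chance of missing such an event. The result assumes independent patients with a common event rate, which is the model the protocol's own per-cohort table follows, and full enrolment of 14 per cohort.

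The per-cohort table is right for 14 to about one point and needs only a label. Because the study is exploratory and nothing operational rests on these figures, this is a clear but modest error in a stated design property.

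**What to change.** In protocol section 8.2:
- Change the pooled sentence from 94% to about 88%.
- Change the pooled table for n=42 to 88% / 98.8% / 99.9% at true rates of 5% / 10% / 15%.
- Label the per-cohort table n=14 enrolled and print 51 / 77 / 90 / 96%. This is preferable to recomputing it for 12 (46 / 72 / 86 / 93%), because safety is analysed in all dosed patients.
- Use the corrected figures if these statements are carried into a study report.

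The cost is a correction to text and tables. Enrolment, treatment and analyses do not change; the stated detection chance becomes somewhat less favourable.

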8.3 POPULATION ANALYSIS

The data from randomized patients who did not receive any study medication will be excluded from the statistical analysis and will only be listed individually in the Appendix of the final study report.

The following data subsets will be analyzed:

Safety analysis subset (SAS)

The safety analysis set will include all randomized patients who have received at least one dose of active treatment.

Full analysis subset (FAS)

The term “full analysis subset” is used to describe the analysis set which is as complete as possible and as close as possible to the intention-to-treat (ITT) ideal of including all randomized patients.

The full analysis set will comprise all randomized patients who have received at least one dose of active treatment and who provide any follow-up data for the primary target variables.

Per protocol subset (PP)

The basis of PP subset is the full analysis set.

Handling of drop-outs and missing values will be performed as for the full analysis dataset. Protocol deviations excluding patients from the Per Protocol analysis set will be defined in the statistical analysis plan and will include failure to satisfy inclusion or exclusion criteria, taking any not permitted concomitant medication during the study, serious non-compliance.

8.3.1 Background and Demographic Characteristics

Assessments made at the screening and baseline visits will be summarized by treatment group. These assessments will include demographic characteristics and other relevant parameters and prognostic factors. By-treatment summaries will serve to identify any imbalances between the treatment groups at baseline. Summary tables will be provided for the full analysis set, for the per-protocol analysis set and for the safety analysis set by means of descriptive statistics and frequency tables, where appropriate. In accordance with Altman, no significance tests will be performed to assess baseline comparability.

8.3.2 Study Medication

For each patient, the individual extent of exposure will be calculated in terms of:

- Total duration of treatment

OPKO Biologics	Protocol for Clinical Study CP-4-004	Page 95 of 133
Effective Date: Date of final electronic approval		

- Total dose

These variables will be listed by patient, sorted by treatment group and patient number. Summary statistics per treatment group will be tabulated.

Study drug compliance will be calculated as specified in the Statistical Analysis Plan. It will be listed by patient and presented for the FAS and the PP set by means of summary statistics by treatment group.

8.3.3 Concomitant Therapy

Previous and current medication will be summarized by counts and percentages, overall (any previous or current medication) and per WHO-DRL category. This table will include those medications reported on the “Previous and current medication (all visits)” CRF, which have a stop date prior to the date of first administration of study medication. All other medication entered on these CRF pages will be considered as concomitant medication.

Previous and current non-medicinal therapy will be handled and tabulated in the same way as specified above for previous and current medication.

8.4 EFFICACY EVALUATION

The secondary and [REDACTED] efficacy endpoints related to IGF-I and IGFBP-3 assessments will be subsumed under biochemical endpoints and may serve as pharmacodynamic endpoints.

EFFICACY ENDPOINTS:

Primary endpoints (Main study):

- Annual Height Velocity in cm/year at 12 months (Baseline Visit – Visit 1).

Secondary endpoints (Auxology/Clinical) (Main study):

- Height velocity at 6 months (Baseline Visit – Visit 1);
- Delta height SDS at 6 and 12 months (compared to visit 1/Baseline value).

Secondary endpoints (Biochemical) (All study periods):

- Absolute IGF-I levels on day 4 after MOD-4023 dosing;
- IGF-I SDS on day 4 after MOD-4023 dosing.

OLE endpoints (including LT-OLE and LT-OLE-PEN)

- Annual Height Velocity in cm/year at each 12 months interval;
- Delta height SDS every 12 months (compared to the previous value);

OPKO Biologics	Protocol for Clinical Study CP-4-004	Page 96 of 133
Effective Date: Date of final electronic approval		

8.4.1 Methods of Efficacy Analysis

The efficacy analysis will be exploratory, and based upon descriptive summary statistics, confidence intervals, exploratory nature statistical tests and graphical data presentations. For those parameters (IGF-I or other pharmacodynamic parameters subsumed under secondary biochemical endpoints) in which the analysis reveals that a consideration of extent of availability – similar to PK parameters – seems to be a meaningful supplement to the usual descriptive statistics, additionally, appropriate areas under the time-concentration curves may be defined and determined.

The effect of dose or dose group on the primary and secondary efficacy criteria subsumed under biochemical endpoints may be analyzed using ANOVA (analysis of variance) methods.

Primary and secondary clinical endpoints will be calculated using SAS or other validated software and these endpoints may be analyzed using ANOVA methods in order to compare the treatment arms.

The efficacy analysis will be performed based upon the FAS and PP subsets and subgroups based on peak hGH level following stimulation tests.

SAFETY ENDPOINTS: (All study periods)

- Incidence of adverse events;
- Incidence of anti-MOD-4023 antibody formation (including characterization of the antibodies and neutralizing properties);
- Local injection site assessment;
- IGF-I levels;
- Parameters of glucose metabolism: blood glucose, fasting insulin level, HbA1c;
- Thyroid status;
- Lipid parameters;
- Cortisol levels;
- All other hematology and biochemical parameters;
- Physical examination;
- Vital signs.

8.5 SAFETY EVALUATION

The assessment of safety will be based mainly on the frequency of AEs, frequency of anti-MOD-4023 antibody development and on the number of laboratory values that fall outside of laboratory normal ranges. Other safety data (e.g. vital signs, special tests, etc.) will be considered as appropriate.

AEs will be listed by treatment group and patient for the treatment phase. AEs will be summarized by presenting, for each treatment group, the number and percentage of patients having any AE, having an AE in each body system and having each individual AE. Any other

OPKO Biologics	Protocol for Clinical Study CP-4-004	Page 97 of 133
Effective Date: Date of final electronic approval		

information collected (e.g. severity or relatedness to study medication) will be listed as appropriate.

Summaries and analyses will be based on treatment-emergent adverse events (TEAE), which are defined as AEs occurring after the first administration of study medication (as recorded on the study discontinuation / end of study CRF) or AEs present before the first dose and ongoing after administration with increased severity. Other AEs (pre-treatment AEs) will only be listed.

If appropriate, laboratory and/or ECG data will be summarized by presenting shift tables using extended normal ranges (baseline to most extreme post-baseline value), by presenting summary statistics of raw data (means, medians, standard deviations, ranges) and change from baseline values and by the flagging of notable values in data listings.

Blood glucose, HbA1c, cortisol, thyroid panel tests and lipid panel tests (with special attention on LpA) will be evaluated using standard descriptive statistics, the number of patients who had values outside normal values, and by listing values considered clinically relevant by the investigator.

Data from other tests (e.g. blood pressure or vital signs) will be listed, notable values will be flagged, and any other information collected will be listed as appropriate. Summary statistics will be given where appropriate.

In addition the number and percentage of patients developing antibodies, including neutralizing antibodies, will be summarized by cohort.

Local tolerability will be summarized based on the investigator's assessments of pain, tenderness, erythema, warmth and swelling which will be done by a scale and predetermined schedule during intensive PK/PD sampling.

The safety analysis will be performed based upon the safety analysis subset.

